## Table D-2.Bayesian type I error/false positive rate (Error I) and power/true
positive rate for ABBV-105 vs Placebo

\* For sample size = 40:20 (k = 2),  $\alpha = 0.05$ ,  $1 - \beta = 80\%$ ,  $\delta = 0.85$ .

Table D-2 shows the Bayesian type I error rate/false positive rate and power/true positive rate for different number of borrowing and different relative bias (r = 0.1 - 0.6) given sample size = 40:20 (k = 2),  $\alpha = 0.05$ ,  $1 - \beta = 80\%$ ,  $\delta = 0.85$ . For  $r \le 0.4$ , with the sample size = 40:20 (k = 40/20 = 2) for ABBV-105 and placebo respectively, we could borrow up to 20 historical placebo subjects while controlling type I error rate/false positive rate < 10% and not exceeding in study placebo sample size. For example, for r = 0.3, borrowing 20 will control false positive rate at 7%.

Therefore, for this analysis with historical data borrowing, we would borrow historical data:  $n_h = 20$ ,  $\mu_h = -0.80$ , and its SE  $\sigma_h = 1.5/\sqrt{20} = 0.335$ . That is, the prior distribution for placebo would be N (-0.80, 0.335). For ABBV-105, a "flat" non-

informative prior probability distribution will be assumed, that is the posterior distribution is totally from the data.

A supportive analysis will also be performed as dynamic borrowing based on the observed r and Table D-2. For example, if r = 0.2, we will borrow up to 50 historical sample size. On the other hand, if r = 0.5 in positive (+) direction, we just borrow 10; if r = 0.5 in negative (-) direction, we will not borrow (borrow 0). Overall, if borrowing provides a true positive rate above 65% and false positive rate less than 10%, we conduct dynamic historical borrowing by picking up the appropriate borrowing sample size to achieve maximum true positive rate.

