7.6 Sample Size Estimation

The planned total sample size is 240. Forty patients per arm of ABBV-105 can provide approximately 83% power to detect a -0.88 difference in DAS28 (CRP) change from baseline for ABBV-105 vs 20 placebo patients combined with 20 borrowed historical placebo subjects (assuming a placebo mean change from baseline: -0.77, and ABBV-105: -1.65 with common standard deviation [SD] = 1.5) using two group t-test with a 0.05 one-sided significance level. It can provide minimum of 85% power to detect a dose-response model for ABBV-105 and combined placebo from 6 candidate models: Linear (δ = 0.01), EMax (ED50 = 5 mg), Exponential (δ = 20), Logistic (ED50 = 5 mg, δ = 10), SigEMax (ED50 = 5 mg, h = 2), and Quadratic (δ = -0.01) using MCP-Mod with a 0.05 one-sided significant level. In the event that placebo variability precludes historic borrowing, comparison using only the in-study 20 placebo patients is still estimated to provide 68% power for pairwise comparison of ABBV-105 vs placebo or a minimum of 70% power in detecting a dose-response model for ABBV-105 and placebo.

The planned sample size of 60 patients treated with ABBV-599 provides about 94% power to detect a -1.0 increase in DAS28 (CRP) LS mean change from baseline for ABBV-599 vs the group of 40 patients treated with ABBV-105 (assuming ABBV-105 mean change from baseline: -1.65 and ABBV-599: -2.65

with common SD = 1.5) using two group t-test with one-sided α = 0.05 significant level. The sample size of 60 for ABBV-599 vs 40 for placebo is over powered due to the necessary power for ABBV-105 over placebo.

The 60 patients for ABBV-599 vs 40 for upadacitinib could extend around 0.5 from observed difference in mean change from baseline for a two-sided 90% confidence interval assuming the common SD = 1.5. Supposing the difference for ABBV-599 vs upadacitinib is -0.45, the 90% confidence interval of (-0.95, 0.05) could be detected with given same size.

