#### • ABBV-105 vs Placebo (Borrowing Placebo)

For placebo control group vs ABBV-105 treatment group, historical data for placebo group are available from three clinical trials at the time of design stage of the current trial. These historical control data consist of 349 subjects from three clinical trials with similar populations (TNF and/or Bio-IR on background MTX or csDMARDs), mechanism of action (JAK inhibition), and study designs: baricitinib Phase 3 study BEACON (n = 176, mean [SD] of DAS28-CRP change = -0.8 [1.5]) [Genovese 2016]; tofacitinib Phase 3 study STEP (n = 118, mean (SD) = -0.6 (1.5)) [Burmester 2013]; and upadacitinib-Phase II (n = 55, mean (SD) = -1.1 (1.6)) (AbbVie Study M13-550). The criteria for

relevant historical control data selection were evaluated and met for these trials and the trial under design. These studies have similar population (TNF and Bio-IR), similar inclusion and exclusion criteria and were conducted in the similar way as the current study as shown in Table D-1.

		Current Study			
Criteria	Baricitinib (BEACON P3)	Tofacitinib (STEP P3)	Upadacitinib (M13-550 P2)	ABBV-599 (M16-063 P2)	
Inc 1	Bio-IR	Bio-IR	Bio-IR	Bio-IR	
Inc 2	18 years or older	18 years or older	18 years or older	18 years or older	
Inc 3	Moderately to severely RAModerately to severely RAModerately to severely RA		Moderately to severely RA	Moderately to severely RA	
Inc 4	csDMARDs	Methotrexate	Methotrexate	csDMARDs	
Exc 1	haemoglobin < 100 g/L	haemoglobin < 90 g/L	haemoglobin < 90 g/L	haemoglobin < 90 g/L	
Exc 2	WBC < 2.5 × 10^9/L	WBC < 3.0 × 10^9/L	WBC < 3.0 × 10^9/L	WBC < 3.0 × 10^9/L	
Exc 3	platelet < 100 × 10^9/L	platelet < 100 × 10^9/L	platelet < 100 × 10^9/L	platelet < 100 × 10^9/L	
Exc 4	eGFR < 40 mL/min/ 1.73 m^2	eGFR < 40 mL/min/ 1.73 m^2	eGFR < 40 mL/min/ 1.73 m^2	eGFR < 40 mL/min/ 1.73 m^2	
Exc 5	AST/ALT > 1.5 × ULN	$AST/ALT > 1.5 \times ULN$	$AST/ALT > 1.5 \times ULN$	$AST/ALT > 2 \times ULN$	

 Table D-1.
 Major entry criteria for historical studies and Study M16-063

The meta-analysis shows that predicted estimated mean (SD) and 95% confidence interval for mean are -0.80 (1.5) and [-1.06, -0.54] (Figure D-1) based on Empirical Bayes estimator [Sidik 2007]. The estimated heterogeneity variance  $\tau^2 = 0.0297$  and historical effective sample size (the maximum number of subjects we could borrow) is 49 [Neuenschwander 2010].

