#### D-2 Borrowing size and prior distribution determination

For the primary analysis, our principle for fixed borrowing historical sample size is not to exceed the sample size in the current study. For placebo control borrowing, the fixed historical placebo borrowing sample size will not exceed 20. The upadacitinib fixed historical borrowing will not exceed 40.

• ABBV-105 vs Placebo (Borrowing Placebo)

Assume the mean for ABBV-105 is -1.65 and for placebo is -0.80 (from meta-analysis) so the absolute effect size is  $\delta = 0.85$ . Let *r* define the relative bias from historical data, i.e.,  $|\mu_C - \mu_h| = r\delta$  where  $\mu_C$  is the true but unknown mean for control group (placebo) and  $\mu_h$  is the historical data mean calculated from meta-analysis. To assess the bias impact on historical data borrowing, a reasonable limit for bias  $r\delta$  would be the half confidence interval width from meta-analysis i.e.,  $r\delta \leq 0.26$ . So

$$r \le 0.26/0.85 = 0.31.$$

Let  $a_0 = \frac{n_h}{n_h + n_c}$  be the proportion of borrowed number of historical patients  $(n_h)$  among all control patients  $(n_h + n_c$  where  $n_c$  is the number of control group subjects in current study). Let  $\mu_T$  and  $n_T$  be the treatment group mean and the number of subjects. Given r, and  $a_0$ , we can obtain Bayesian type I error rate/false positive rate (i.e., the probability achieving  $P(\mu_T - \mu_c < 0|Data) > 1 - \alpha$  under the null hypothesis  $\mu_T = \mu_c$ ):

$$\Phi\left[\frac{\pm\sqrt{2}ra_0\left(\Phi^{-1}(1-\alpha)+\Phi^{-1}(1-\beta)\right)-\Phi^{-1}(1-\alpha)\sqrt{1+k(1-a_0)}}{\sqrt{1+k(1-a_0)^2}}\right] \tag{1}$$

and Bayesian power/true positive rate (i.e., the probability achieving  $P(\mu_T - \mu_C < 0 | Data) > 1 - \alpha$  under the null hypothesis  $\mu_C - \mu_T = \delta$ ):

$$\Phi\left[\frac{\sqrt{2}(1\pm ra_0)\left(\Phi^{-1}(1-\alpha)+\Phi^{-1}(1-\beta)\right)-\Phi^{-1}(1-\alpha)\sqrt{1+k(1-a_0)}}{\sqrt{1+k(1-a_0)^2}}\right].$$
 (2)\*

The  $\pm$  in above formula corresponds to two directions of the bias,  $\alpha$  and  $1 - \beta$  are type I error and power for sample size calculation without borrowing, and  $k = n_T/n_C$  is the randomization ratio in current study with reduced control group due to borrowing.

\* (1) and (2) could be derived as follows:

Probability of trial success =  $P(P(\mu_T - \mu_C < 0 | Data) > 1 - \alpha)$ 

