In addition, a supportive analysis using dynamic borrowing will also be performed based on the observed r and extended Table D-3 (not presented). For example, if bias is positive and r = 0.6, we could borrow 50 historical sample size to control false positive rate within 10%. On the other hand, if bias is negative, we will not borrow (borrow 0). Overall, if borrowing provides a true positive rate above 34% and the false positive rate less than 10%, we conduct dynamic historical borrowing by picking up the appropriate borrowing sample size to achieve maximum true positive rate.

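### The supportive dynamic-borrowing rule for ABBV-105 vs placebo enters a table built for the true bias with the observed bias, so the tabulated false-positive limit of 10% does not carry over

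*SAP*

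**What the plan says.** The main borrowing analysis uses a fixed size. SAP Appendix D-2 states that "the fixed historical placebo borrowing sample size will not exceed 20", with a corresponding limit of 40 for upadacitinib. Table D-2 supports the choice of 20. It gives false-positive and true-positive rates by number borrowed and by r, where r times 0.85 is the distance between the historical mean and the true, unknown control mean. The SAP takes r up to 0.31 as the reasonable range (half-width 0.26 of the meta-analysis interval, divided by 0.85). It claims control below 10% with 20 borrowed for r up to 0.4.

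A supportive analysis then uses "dynamic borrowing based on the observed r and Table D-2". Borrowing is allowed where the tabulated power exceeds 65% and the tabulated false-positive rate is below 10%, and the size with the most power is chosen. The worked example goes up to 50 at r = 0.2. Appendix D-1 says of the placebo data that the "historical effective sample size (the maximum number of subjects we could borrow) is 49".

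For ABBV-599 vs upadacitinib the same approach uses a power threshold of 34% and an extended Table D-3 that is not shown, with the added instruction that "if bias is negative, we will not borrow (borrow 0" subjects). SAP Section 8.3.5.2 says dynamic borrowing may be done; Appendix D says it will be. No operating characteristics of the dynamic rule itself are given.

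**The concern.** Table D-2 answers this question: if the true bias is r and a fixed number is borrowed, how often is a false positive declared? The dynamic rule poses a different one. The in-study placebo mean first selects the number borrowed and then enters the test. When chance makes placebo look close to history, the rule borrows heavily whatever the true bias is. A limit read from the table at the observed r is therefore not a limit on the error of the procedure.

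At stake is how the supportive result is read. If it is presented as held below 10%, it will look at least as safe as fixed borrowing of 20. Over the SAP's plausible range, when the bias is in the inflating direction, it is more liberal.

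**Working it through.** **Inputs.** One-sided alpha 0.05 (Protocol 7.6: "using two group t-test with a 0.05 one-sided significance level"; Appendix D-3: posterior probability above 0.95). Table D-2 footnote: "For sample size = 40:20 (k = 2"), design power 80%. Appendix D-2: "Assume the mean for ABBV-105 is -1.65 and for placebo is -0.80", so delta = 0.85. Appendix D-1: "predicted estimated mean (SD) and 95% confidence interval for mean are -0.80 (1.5").

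**Step 1: reproduce Table D-2.** SAP formula (1) with r = 0.3 in the + direction and 20 borrowed has a0 = 20/40 = 0.5. The normal quantiles are 1.645 and 0.842, sum 2.486.
- Numerator: 1.414 × 0.3 × 0.5 × 2.486 − 1.645 × √(1 + 2 × 0.5) = 0.527 − 2.326 = −1.799.
- Denominator: √(1 + 2 × 0.25) = 1.225.
- Φ(−1.469) = 0.071, the printed value.

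All cells of Table D-2 reproduce within 0.0005.

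**Step 2: precision of the observed r.** SE = (1.5/√20)/0.85 = 0.335/0.85 = 0.39.

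**Step 3: what the rule selects.** In the + direction the table leads to 50 borrowed at r = 0.1 and 0.2, 40 at 0.3 (tabulated 0.099), 20 at 0.4 (0.093), and 10 at 0.5 (0.080) and 0.6 (0.094). In the − direction it leads to 50 up to r = 0.4 and none at 0.5. If the true r is 0.4, the observed r lies between −0.4 and 0.2 with probability Φ(−0.51) − Φ(−2.03) = 0.306 − 0.021 = 0.285. In those trials 50 are borrowed, a size for which Table D-2 itself gives 16.3% at r = 0.4.

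**Step 4: actual error of the rule.** Let x be the in-study placebo mean, distributed N(μC, 1.5²/20), and n_h(x) the size chosen from {0, 10, …, 50}. The posterior control mean is m(x) = (20x + n_h μh)/(20 + n_h). The test uses SE(x) = 1.5 √(1/40 + 1/(20 + n_h)). Under μT = μC,

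error = ∫ Φ{[m(x) − 1.645 SE(x) − μC] / (1.5/√40)} f(x) dx.

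Here + means that the historical mean shows less improvement than the true control mean, which is the inflating direction in the tables.

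| true r (+) | dynamic, to 50 | dynamic, capped at 20 | fixed 20, formula (1) |
|---|---|---|---|
| 0 | 5.7% | 5.3% | 2.9% |
| 0.31 | 10.2% | 7.7% | 7.3% |
| 0.4 | 12.1% | 9.1% | 9.3% |
| 0.5 | 13.9% | 10.6% | 11.9% |
| 0.6 | 14.9% | 11.9% | 15.0% |

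The uncapped rule peaks at 15.0% near r = 0.65. A simulation of 2,000,000 draws agreed with the integration (5.7%, 10.0% and 13.9% at r = 0, 0.3 and 0.5). Other readings of the rule (r rounded or continuous, integer sizes to 49 or 50, no borrowing beyond r = 0.6) put the peak between 14.1% and 16.7%. With 40:20 and SD 1.5 entered directly, fixed borrowing gives 7.4% at r = 0.31 and 9.4% at 0.4. The small gap arises because formula (1) implies 2 × 2.486² × 1.5²/0.85² = 38.5 treated subjects, not 40.

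**Step 5: upadacitinib.** Borrowing only for positive observed bias moves the control mean towards a larger ABBV-599 advantage each time it is used. With no true bias the average shift is about 0.035 DAS28 (sizes to 50) to 0.04 (sizes to 200), roughly 10–12% of the assumed 0.33. At the SAP's limit r = 0.65 the error is 7.7% to 9.4% (SD 1.57, same two grids), against 9.3% in Table D-3 for fixed borrowing of 40. At SD 1.5 with any integer size up to 206 it reaches 10.1%. The 34% rule applied alone would still borrow for small negative bias: up to about r = 0.2 on a grid to 50, and about 0.3 on a grid to 206.

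**The case against.** A reader might infer that the rule's error is 15%. That figure needs r near 0.65, about twice the SAP's plausible limit. At the limit itself the excess over 10% is 0.2 points. Beyond r = 0.6 fixed borrowing of 20 is worse (formula (1) gives 18.6% at r = 0.7, against 15.0% for the dynamic rule), so the dynamic rule does bound the damage from large bias. This stands. What remains is that the SAP itself speaks of control below 10% up to r = 0.4 and works dynamic examples at r = 0.5, where the rule gives 12.1% and 13.9%.

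A reader might also infer that the upadacitinib rule breaches 10%. At its stated limit it is similar to, or below, fixed borrowing of 40. Its one-sidedness has a disclosed reason: every borrowing cell on the negative side of Table D-3 has power below 34%. Forcing borrowing in both directions would conflict with that criterion and barely changes the error.

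Nor does borrowing 50 break the limits of 20 and 40, which the SAP applies to fixed borrowing in the primary analysis. The one real conflict on size is 50 against 49, a single subject.

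Finally, the analysis is supportive. SAP Section 8.3.5.1 gives comparisons without borrowing, Section 8.3.5.3 gives a dose-response sensitivity analysis with the unborrowed placebo estimate, and the ranked tests in Section 12.0 do not use dynamic borrowing. That limits the consequence, but the error limit still does not describe this rule.

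**Conclusion.** The point holds for the placebo rule. The false-positive limit of 10% taken from Table D-2 does not apply to a borrowing size chosen from the observed r. The actual rate is about twice that of fixed borrowing of 20 when there is no bias, just over 10% at r = 0.31 and about 12% at r = 0.4. The dynamic rule is the more liberal of the two up to r of about 0.5.

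This rests on SD 1.5, arms of 40 and 20, normal means, sizes in tens up to 50, and + as the inflating direction. The sign has to be assumed: the SAP defines r by an absolute value, and its printed derivation carries a minus sign on the bias term that does not match the tables. Reversing the sign leaves the placebo result similar (10.2% at r = 0.3, 12.7% at 0.4), but turns the upadacitinib shift away from ABBV-599.

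For upadacitinib the finding is limited to an unreported directional shift and two instructions that conflict for small negative bias. No breach of 10% is claimed there. The primary inference is unaffected.

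**What to change.** 1. In Appendix D-2, replace the table-based limit of 10% for dynamic placebo borrowing with simulated false-positive and true-positive rates that include sampling error in the observed r.
2. Cap dynamic placebo borrowing at 20. The capped rates in the table above still pass 10% at r = 0.5, so even the capped rule should not be described as below 10% for every r.
3. Reconcile borrowing up to 50 with the stated maximum of 49.
4. Define the sign of the bias explicitly and correct the printed derivation to match.
5. For upadacitinib, reconcile the instruction not to borrow for negative bias with the general 34% rule, present the extended Table D-3, and report the shift of about 0.035–0.04 DAS28 at zero bias.
6. State consistently whether the dynamic analysis may or will be done.

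The cost is a short simulation, SAP wording and slightly less power in a supportive analysis. Adding the 0.85 effect inside the braces of the Step 4 integral gives 83.9% power uncapped and 81.1% capped at zero bias.

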#### • ABBV-599 vs Upadacitinib

Assume the mean for ABBV-599 is –2.65 and for upadacitinib is –2.32 so the absolute effect size is  $\delta = 0.33$ . To control the bias with historical data borrowing, a reasonable limit for bias  $r\delta$  would be the half confidence interval width from meta-analysis i.e.,  $r\delta \leq 0.215$  or  $r \leq 0.65$ . With the same formula as for ABBV-105 vs placebo, we obtained the Bayesian type I error/false positive rate and power/true positive rate in Table D-3 for r = 0.6/0.65/0.7, respectively.

Borrowing # of Subjects	r = 0.6				r = 0.65				r = 0.7			
	Error I		Power		Error I		Power		Error I		Power	
	-	+	_	+	_	+	-	+	_	+	_	+
0	0.05	0.05	0.34	0.34	0.05	0.05	0.34	0.34	0.05	0.05	0.34	0.34
10	0.028	0.057	0.298	0.422	0.027	0.059	0.294	0.427	0.026	0.061	0.289	0.432
20	0.018	0.066	0.273	0.497	0.017	0.070	0.264	0.507	0.016	0.073	0.256	0.517
30	0.012	0.076	0.254	0.561	0.011	0.081	0.243	0.574	0.010	0.087	0.233	0.587
40	0.009	0.087	0.241	0.612	0.008	0.093	0.228	0.628	0.008	0.100	0.216	0.643
50	0.007	0.097	0.231	0.654	0.007	0.105	0.217	0.671	0.006	0.114	0.204	0.688

Table D-3.Bayesian type I error/false positive rate (Error I) and power/true
positive rate for ABBV-599 vs Upa

\* For sample size = 60:40 (k = 1.5),  $\alpha = 0.05$ ,  $1 - \beta = 39\%$ ,  $\delta = 0.33$ .

Table D-3 shows the Bayesian type I error rate/false positive rate and power/true positive rate for different number of borrowing and different relative bias given sample size = 60:40 (k = 1.5),  $\alpha = 0.05$ ,  $1 - \beta = 39\%$ ,  $\delta = 0.33$ . For  $r \le 0.65$  in positive direction, sample size = 60:40 for ABBV-599 and upadacitinib respectively, we could borrow 40 historical placebo subjects while controlling type I error rate < 10% and no more than in study sample size 40. Therefore for historical data borrowing analysis, we have  $n_h = 40$ ,  $\mu_h = -2.32$ , and its SE  $\sigma_h = 1.57/\sqrt{40} = 0.25$ . That is, the prior distribution for upadacitinib would be  $N(-2.32, 0.25^2)$ . For ABBV-599, a "flat" non-informative prior probability distribution will be assumed. That is the posterior distribution is totally based on the observed data.

In addition, a supportive analysis using dynamic borrowing will also be performed based on the observed r and extended Table D-3 (not presented). For example, if bias is positive and r = 0.6, we could borrow 50 historical sample size to control false positive rate within 10%. On the other hand, if bias is negative, we will not borrow (borrow 0). Overall, if borrowing provides a true positive rate above 34% and the false positive rate less than 10%, we conduct dynamic historical borrowing by picking up the appropriate borrowing sample size to achieve maximum true positive rate.

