7.3 Statistical Analyses for Efficacy

Primary Endpoint Analysis

The primary endpoint is change from baseline in DAS28-CRP at Week 12.

The first primary analysis is to test the superiority of ABBV-599 compared to placebo at Week 12.

The second primary analysis is to test a pre-specified set of dose-response models (detailed in the SAP) among ABBV-105 dose groups and the placebo group at Week 12 using the Multiple Comparison Procedure – Modeling (MCP-Mod) method.^{9,10}

Hypothesis testing in the primary analyses will be performed in a ranked fashion based on one-sided significance level of α = 0.05. The other analysis for the primary endpoint includes testing the superiority of ABBV-599 compared to each ABBV-105 dose group, as well as to upadacitinib. Additionally, each ABBV-105 group will be compared vs placebo group. All tests will be performed as

pairwise comparison at one-sided statistical significance level α = 0.05. The listing of these analyses is as follows:

- ABBV-599 vs placebo
- ABBV-105 dose response
- ABBV-599 vs each ABBV-105 dose
- Each ABBV-105 dose vs placebo
- ABBV-599 vs upadacitinib

In the analyses, the treatment mean will be estimated using least squares (LS) mean from Mixed-Effect Model Repeated Measurements (MMRM) method. One MMRM model including all treatment groups up to visit Week 12 data modeling will be used. Comparable historical placebo and upadacitinib data will be used to enhance the statistical power in relevant comparison analyses, which are detailed in the SAP.

Secondary Endpoints Analysis

Continuous efficacy variables will be analyzed using an MMRM method. It will be used for primary inference purpose. Categorical efficacy variables will be analyzed using the Cochran-Mantel-Haenszel (CMH) test controlling for stratification variables. Non-responder imputation (NRI) will be used for primary inference purpose and as observed (AO) analyses will be used for sensitivity analysis for selected endpoints.

Missing Data Imputation Definition

Non-Responder Imputation: An NRI approach will categorize any subject who has missing value for categorical variables at a specific visit as non-responder for that visit. In addition, subjects who prematurely discontinue from study drug will be considered as non-responders for all subsequent visits after discontinuation.

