## 2.4 Sample Size Determination

The planned total sample size is 240. Forty (40) patients per arm of ABBV-105 can provide approximately 83% power to detect a –0.88 difference in DAS28 (CRP) change from baseline for ABBV-105 vs placebo combined with 20 borrowed historical placebo subjects (assuming a placebo mean change from baseline –0.77, and ABBV-105: –1.65 with common SD = 1.5) using two group t-test with one-sided significant level  $\alpha = 0.05$ . It can provide a minimum of 85% power to detect a dose-response model for ABBV-105 and combined placebo from 6 candidate models: Linear,

EMax (ED50 = 5 mg), Exponential ( $\delta$  = 20), Logistic (ED50 = 5 mg,  $\delta$  = 10), SigEMax (ED50 = 5 mg, h = 2), and Quadratic ( $\delta$  = -0.01) using MCP-Mod with one-sided significant level  $\alpha$  = 0.05.

The planned sample size of 60 patients treated with ABBV-599 provides approximately 94% power to detect a -1.0 difference in DAS28 (CRP) LS mean change from baseline for ABBV-599 vs the group of 40 patients treated with ABBV-105 (assuming ABBV-105 mean change from baseline: -1.65 and ABBV-599: -2.65 with common SD = 1.5) using two group t-test with one-sided significance level  $\alpha = 0.05$ . The sample size of 60 for ABBV-599 vs 20 for placebo is over-powered due to the necessary power for ABBV-105 over placebo.

The sample size of 60 patients for ABBV-599 vs 40 for upadacitinib could produce the half width of 0.5 in the two-sided 90% CI of the difference in mean change from baseline, assuming the common SD = 1.5. Assuming the observed difference for ABBV-599 vs upadacitinib is -0.45, the corresponding 90% confidence interval would be (-0.95, 0.05).

In the event that placebo variability precludes historic borrowing, comparison using only the in-study 20 placebo patients is estimated to still provide 68% power for pairwise comparison of ABBV-105 vs placebo and a minimum of 70% power in detecting a dose-response model for ABBV-105 and placebo.

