### • ABBV-599 vs upadacitinib (Borrowing upadacitinib)

For the upadacitinib control group versus ABBV-599, historical data consist of 206 subjects from two upadacitinib studies (Phase 2: Study M13-550 Balance I and Phase 3: Study M13-542 Select Beyond). Active upadacitinib treatment group of 15 mg is considered. The meta-analysis results in the predicted estimated mean (SD) and 95% confidence interval are -2.32 (1.57) and [-2.54, -2.11].

For this comparison, 40 historical placebo subjects will be borrowed, which targets control of false positive rate < 10% and not exceeding the study sample size 40. That is:  $n_h = 40$ ,  $\mu_h = -2.32$ , and  $\sigma_h = 1.57/\sqrt{40} = 0.25$ . Therefore the prior distribution for upadacitinib would be  $N(-2.32, 0.25^2)$ . For ABBV-599, a "flat" non-informative prior probability distribution will be assumed, resulting in the posterior distribution totally based on the data. A dynamic borrowing based on observed bias may be performed as supportive analysis.

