$$= \Phi\left(\frac{\mu_{c} - \mu_{T}}{\sigma\sqrt{\frac{1}{n_{T}} + \frac{1 - a_{0}}{n_{h} + n_{c}}}} - \frac{a_{0}(\mu_{h} - \mu_{c})}{\sigma\sqrt{\frac{1}{n_{T}} + \frac{1 - a_{0}}{n_{h} + n_{c}}}} - \Phi^{-1}(1 - \alpha)\frac{\sqrt{\frac{1}{n_{T}} + \frac{1}{n_{h} + n_{c}}}}{\sqrt{\frac{1}{n_{T}} + \frac{1 - a_{0}}{n_{h} + n_{c}}}}\right)$$

The treatment group sample size  $n_T = \frac{2(\Phi^{-1}(1-\alpha)+\Phi^{-1}(1-\beta))^2 \sigma^2}{\delta^2}$  which is the balanced sample size without borrowing. With  $k = n_T/n_c$ , the power without borrowing equals

$$\Phi\left[\sqrt{\frac{2}{1+k}}\left(\Phi^{-1}(1-\alpha)+\Phi^{-1}(1-\beta)\right)-\Phi^{-1}(1-\alpha)\right].$$

With  $k = n_T/n_C$ ,  $|\mu_C - \mu_h| = r\delta$  and  $a_0 = \frac{n_h}{n_h + n_c}$ , (1) could be derived for  $\mu_T - \mu_C = 0$  and (2) could be obtained from  $\mu_C - \mu_T = \delta$ .

		r =	0.1			r = 0.2			r = 0.3			
Borrowing # of	Err	or I	Por	wer	Err	or I	Po	wer	Err	or I	Po	wer
Subjects	_	+	_	+	_	+	_	+	_	+	_	+
0	0.05	0.05	0.65	0.65	0.05	0.05	0.65	0.65	0.05	0.05	0.65	0.65
10	0.028	0.041	0.741	0.793	0.023	0.049	0.712	0.816	0.019	0.058	0.682	0.838
20	0.021	0.040	0.796	0.868	0.014	0.053	0.753	0.896	0.010	0.071	0.706	0.920
30	0.018	0.041	0.831	0.907	0.011	0.060	0.780	0.934	0.007	0.085	0.722	0.955
40	0.016	0.044	0.853	0.929	0.010	0.067	0.798	0.954	0.005	0.099	0.734	0.971
50	0.016	0.047	0.868	0.943	0.009	0.074	0.811	0.965	0.005	0.113	0.742	0.980
		r =	0.4		r = 0.5			r = 0.6				
Borrowing # of	Err	or I	Po	wer	Err	or I	Po	wer	Err	or I	Po	wer
Subjects	_	+	_	+	_	+	_	+	-	+	-	+
0	0.05	0.05	0.65	0.65	0.05	0.05	0.65	0.65	0.05	0.05	0.65	0.65
10	0.015	0.069	0.651	0.858	0.012	0.080	0.619	0.876	0.010	0.094	0.587	0.893
20	0.007	0.093	0.655	0.939	0.004	0.119	0.600	0.954	0.003	0.150	0.544	0.967
30	0.004	0.118	0.657	0.970	0.002	0.158	0.588	0.980	0.001	0.206	0.515	0.988
40	0.003	0.142	0.660	0.982	0.001	0.195	0.579	0.990	0.001	0.258	0.495	0.994
50	0.002	0.163	0.662	0.989	0.001	0.227	0.573	0.994	0.000	0.303	0.481	0.997

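### Table D-3 (ABBV-599 vs upadacitinib) rests on a 39% base power that the SAP's own formula does not give, so its printed powers are too high; the fixed borrowing of 40 is unaffected.

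*SAP*

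**What the plan says.** SAP Appendix D, D-2, evaluates borrowing with two closed formulas, (1) for the false positive rate and (2) for power. Their inputs α and 1 − β "are type I error and power for sample size calculation without borrowing". The derivation ties 1 − β to the treatment-arm size through n_T = 2(z_α + z_β)²σ²/δ², "which is the balanced sample size without borrowing". The base power is therefore fixed once n_T, δ, σ and α are given.

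For this comparison the same section says: "Assume the mean for ABBV-599 is –2.65 and for upadacitinib is –2.32", so δ = 0.33. The Table D-3 footnote gives 60:40 allocation (k = 1.5), α = 0.05 and 1 − β = 39%. It gives no SD.

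The table is used in two ways:

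- **Fixed borrowing.** SAP 8.3.5.2 borrows 40 historical subjects, "which targets control of false positive rate < 10% and not exceeding the study sample size 40". This gives the prior N(−2.32, 0.25²).
- **Dynamic borrowing.** The end of D-2 describes a supportive analysis that reads the borrowing size from the observed r and an extended Table D-3 that is not printed. It borrows "if borrowing provides a true positive rate above 34% and the false positive rate less than 10" percent, choosing the size with the highest power. If the bias is negative, nothing is borrowed.

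**The concern.** The 39% looks too high for 60 subjects per arm and a difference of 0.33 on a scale with an SD near 1.5. Every cell of Table D-3 with borrowing, and the 0.34 in its zero-borrowing row, depends on that input, as does the 34% threshold. Protocol 4.2 includes the upadacitinib arm to estimate what the combination adds to upadacitinib alone. A reader faced with an inconclusive result for this comparison would look to Table D-3 to judge how likely that was. The dynamic rule would also read its borrowing size from cells computed with the wrong input.

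**Working it through.** **Inputs.** One-sided α = 0.05 (Protocol 7.3: "pairwise comparison at one-sided statistical significance level α = 0.05"), so z = 1.645. n_T = 60, n_C = 40, k = 1.5 and δ = 0.33 (SAP D-2). SD is 1.5 from SAP 2.4 ("assuming the common SD = 1.5"), or 1.57 from the historical upadacitinib data and the prior (SAP 8.3.5.2 and Appendix D). Write S = z_α + z_β.

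**1. Reproduce the printed table from 39%.** z_β = −0.279, so S = 1.3655.

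- No borrowing, 60:40: Φ[√(2/2.5) × 1.3655 − 1.645] = Φ(−0.423) = 0.336, printed as 0.34.
- 40 borrowed (a₀ = 0.5), r = 0.65, positive direction. The shared terms are 1.645 × √1.75 = 2.176 and √1.375 = 1.1726.
  - False positive rate: Φ[(√2 × 0.65 × 0.5 × 1.3655 − 2.176)/1.1726] = Φ[(0.628 − 2.176)/1.1726] = 0.093.
  - Power: Φ[(√2 × 1.325 × 1.3655 − 2.176)/1.1726] = Φ[(2.559 − 2.176)/1.1726] = 0.628.

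Both match. The remaining cells agree to within 0.001, apart from the rounding of 0.336 to 0.34. The formulas were applied correctly to the 39%.

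**2. Derive the base power from the SAP's definition.** S = δ√(n_T/2)/σ.

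- SD 1.5: S = 0.33 × √30/1.5 = 1.205; Φ(1.205 − 1.645) = 33.0%.
- SD 1.57: S = 0.33 × √30/1.57 = 1.151; Φ(1.151 − 1.645) = 31.1%.

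**3. Check the reading on Table D-2.** n_T = 40, δ = 0.85 and SD 1.5 give S = 0.85 × √20/1.5 = 2.534 and Φ(0.889) = 81.3%, against 80% stated. That is close, so the gap is specific to Table D-3.

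**4. Look for a route to 39%.** Results are for SD 1.5 and 1.57 respectively.

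- t-test: 32.8%, 30.9%.
- Two-sided 0.05: 22.5%, 20.9%.
- One-sided 0.10: 46.9%, 44.8%.
- 60 vs 80 (40 in-study plus 40 borrowed): 36.1%, 33.9%.

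Reaching 39% needs an SD of about 1.32, or δ of about 0.374 or 0.391, or about 77 or 84 per arm. An SD of 1.3 would give about 40%, and 34% at 60:40. The documents give 1.3 only for placebo subjects in the upadacitinib Phase III study, not for this comparison.

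**5. Recompute Table D-3** (r = 0.65):

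| Quantity | Printed | SD 1.5 | SD 1.57 |
|---|---|---|---|
| Power, 0 borrowed | 0.34 | 0.285 | 0.269 |
| Power (+), 40 borrowed | 0.628 | 0.528 | 0.494 |
| Power (−), 40 borrowed | 0.228 | 0.191 | 0.179 |
| False positive (+), 40 borrowed | 0.093 | 0.083 | 0.080 |
| False positive (−), 40 borrowed | 0.008 | 0.010 | 0.011 |
| False positive (+), 50 borrowed | 0.105 | 0.093 | 0.089 |

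The SAP's general expression for the probability of success gives the same recomputed positive-direction rates and powers.

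**6. Effect on dynamic borrowing.** Largest size with a false positive rate below 10%, positive direction:

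| r | From 39% | SD 1.5 | SD 1.57 |
|---|---|---|---|
| 0.60 | 53 | 68 | 74 |
| 0.65 | 45 | 58 | 63 |
| 0.70 | 39 | 50 | 54 |

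**The case against.** The strongest reply accepts the arithmetic but says that little follows from it. Most of that stands.

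- **Fixed borrowing.** A reader might infer that borrowing 40, or the prior, is no longer justified. It is. The recomputed false positive rate at r = 0.65 is 0.083 or 0.080, below the 10% limit, and the cap at the in-study 40 does not depend on base power. In the positive direction, where inflation is the risk, the printed table is cautious.
- **The 34% threshold.** A reader might infer that a wrong threshold leads to wrong borrowing decisions. Under the SAP's rule it does not. Negative bias means no borrowing. For positive bias with r from 0 to 2, if sizes up to the 206 historical subjects may be chosen, the recomputed power at the selected size is never below 0.449 (SD 1.5) or 0.420 (SD 1.57). Only the 10% limit decides.
- **Sample size.** A reader might infer that the trial's power claim for this comparison fails. Neither Protocol 7.6 nor SAP 2.4 makes one. Both justify 60 vs 40 by a 90% interval half-width of about 0.5, and their example interval includes zero. Table D-3 as printed already shows low power.
- **Standing of the analysis.** The comparison is an additional analysis outside the ranked tests. Dynamic borrowing is supportive: SAP 8.3.5.2 says it may be done, Appendix D that it will be. The SAP's own example (r = 0.6, borrow 50) still meets the limit at 0.086 or 0.082.
- **Which SD.** The documents use 1.5 for the design and 1.57 for the prior, and do not say which one underlies Table D-3. Insisting on either goes beyond the text. A column for zero bias would be a preference, since Table D-2 has none either.

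The reply does not rescue the 39%, the printed powers, or the sizes that the dynamic rule would select.

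**Conclusion.** The point holds as a correction to one input of an appendix table. The 39% contradicts the SAP's own definition, which gives 33.0% or 31.1%. The no-borrowing power is overstated by 5 to 7 percentage points. With 40 borrowed at r = 0.65 (+), power is overstated by 10 to 13 points (0.628 against 0.528 or 0.494). In the dynamic analysis at r = 0.65 (+), the largest admissible size moves from about 45 to 58 or 63, so the printed table leads to less borrowing than the rule would allow.

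This rests on reading 1 − β as the SAP defines it and on an SD of 1.5 or 1.57. It does not reach the two ranked primary tests, the fixed borrowing of 40, or the prior N(−2.32, 0.25²).

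**What to change.** In Appendix D, state the SD behind Table D-3. Recompute Table D-3 and the extended table with the base power that follows: 33% at SD 1.5 or 31% at SD 1.57. If another SD was intended, name it and justify it. For consistency, restate the 34% threshold as the recomputed no-borrowing power (28.5% or 27%), although this is not expected to change a borrowing decision. The fixed borrowing size and prior need no change.

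The cost is rerunning one formula and editing one table, its extended version and one threshold. The stated power for this comparison becomes less favourable. The change is best made before unblinding, so that the dynamic rule is not revised with results in hand.
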